### **9.1.1.3 Validity of Vaccine Exposure**

The precision and sensitivity of COVID-19 vaccine records included in the BIFAP's Table of Vaccine are not known. However, high precision and sensitivity have been estimated for other vaccinations recorded in that table

- after manual revision (against free text comment for human papillomavirus vaccination)(2) or
- validated against expected coverages (as in the Spanish recommended schedules) or external sources (such as other European countries with public

vaccination programs) for vaccinations against human papillomavirus, pertussis, influenza or meningococcus (3).

The information about the COVID vaccinations included in that Table is the result of linking all vaccination registries with the public PC eHR. That link has been strongly recommended (and it is compulsory) by the Ministry of Health and it is used by the Ministry to provide the official coverages since the vaccination campaigns started.

Vaccination data for each patient will include the vaccination date, dose, name of the vaccine, brand and batch for each jab.

Even though, the vaccinations records of the initial priority population for vaccination (i.e. frontline health and social care workers, residents in a care home and patients with special needs) will be available in BIFAP, we will not study them since we expect not enough quality criteria of the baseline consultations to the PCP. Thus, as aforementioned the current study will be restricted to populations where both, vaccination status and baseline and updated clinical history, can be accurately identified.

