#### **9.1.1.4 Definition of Time Zero**

In studies of vaccinated versus unvaccinated persons, researchers must determine the appropriate time point at which to identify patients and begin follow-up. Aligning the evaluation of eligibility criteria, covariate assessment, exposure assignment, and beginning of follow-up (time zero) avoids selection bias and immortal person-time bias and addresses a well-defined study question [13].

Time zero is the time when the vaccination status is assigned; all eligibility criteria must be fulfilled at that point, and COVID outcomes must start to be counted at that point [14].

Time zero in the vaccinated group will be the date when the 1st dose of COVID-19 vaccine is administered (i.e. recorded). That date will be also used for the unvaccinated pairs as Time zero.

The aim of the **Main analysis** will be the estimation of the effectiveness  $\geq 15$  days after full vaccination series whether 1- or 2-doses regimens (and regardless of delayed completion of 2-dose vaccine series ,i.e. recorded dates will be accepted as real world data even though the time between doses are not fully adjusted to recommended intervals). Analysis will be performed by vaccine brand.

In order to properly observe the moment when the effect of the vaccination starts, the period between 1st Dose and 14 days after the 2nd dose will be divided and compared with unvaccinated patients. Thus, at least 5 cut-of periods will be identified along each patient's follow-up contribution:

- 1) Non-exposed period among Unvaccinated patients (Reference for Effectiveness estimation)

- 2) D1-induction time: up-to 14 days after 1st dose
- 3) D1-effectiveness: 15 days after 1st dose to 2nd dose
- 4) D2-induction time: up-to 14 days after 2nd dose
- 5) D2-effectiveness in the short run: 15-90 days after 2nd dose
- 6) D2-effectiveness in the medium run: 91-180 days after 2nd dose
- 7) D2-effectiveness in the long run:  $\geq 181$  days after 2nd dose

[figure not shown]

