#### **9.7.3.2 Adjustment for Confounding**

Backward stepwise selection method will be used to identify variables associated with each outcomes according to a level of significance ( $p\text{-exit} \geq 0.1$ ,  $p\text{-entry} < 0.05$ ) for inclusion or exclusion, that could confound the effectiveness estimates and thus adjust the final models.

Confounders will be measured at baseline and updated before each vaccine dose is administrated or every 28 days (in order to update the collection of confounders during the follow-up of both, vaccinated and unvaccinated patients). The adjusted vaccine effectiveness for all the outcomes will be estimated as 1 minus the adjusted HR.

Adjusted time-specific RDs (e.g., RD at 3, 6, 9, 12 months after time zero) will also be tested [38]

Patients receiving one type of vaccine who receive later a dose of another COVID-19 vaccine, will be considered switcher from the date that the last dose was received and analysed as switchers, since such censoring/switch can be informative. Among switchers, each combination of vaccines will be analysed separately.

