### **9.7.5 Missing Data**

Missing data for the information about COVID-19 vaccinations, i.e. date of administration, type/brand of vaccine, dose order (whether 1st or 2nd dose), may happen due the workload. However, due the importance of knowing the effect of the vaccinations in the pandemic we expect the health professional properly record all required data.

The distribution and pattern of missingness (i.e. missing completely at random or missing at random) will be assessed [49]. The pattern missing not at random (MNAR) may be derived from external data on the doses distributed by region and among prioritised groups. If amount of missing is relevant, single stochastic imputation will be performed based on determinant of both, missing data and the value of the variable with missing data. Mainly, calendar month or week, region and prioritised group will be tested as determinant of missing and will established for the imputation. Multiple imputation correcting by the variance is a more complex approach (even more using a time-varying data source) and may not be worthy if simple determinants are identified.

No imputation are planned for missing data in potential confounders (i.e. BMI or smoking use). In order to all individual contribute to the analysis, a missing category will be established for patients with missing data. If those variables suggest poor confusion in the regression models, they will be removed as confounders for the final models [72].

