The validity of coding for future COVID-19 vaccines—including the ability to distinguish between separate products—or COVID-19 outcomes is unknown at this time, and the likelihood of missing data on specific vaccine brand may be high. Misclassification of vaccine exposure, outcome status, or covariates is possible in existing health care data not collected for research purposes. Information about COVID-19 infection (through test results or codes) may not be captured reliably in databases. Additionally, COVID-19 testing is not systematic, and laboratory confirmation of case status may not be available for many patients. Currently, bias may be minimised since COVID 19 testing becomes near universal and repeated with individuals, with similar testing capacity and practice across regions, though. Since we will not have any better gold-standard for case status than the information about confirmed covid-19 infection through lab results (used for case definition in the current study) its precision will not be evaluated but with the expected external incidences published by the Health authorities.

Also, we consider that if COVID misclassification occurred it would be similar in both, vaccinated and unvaccinated groups, however surveillance or detection bias (different likelihood of screening or testing for COVID between the groups) cannot be discarded. If vaccinated individuals had less likelihood of screening or test than unvaccinated, we would artificially observe more cases among unvaccinated, directing toward a biased higher vaccine effectiveness estimation.

Data from multiple regions and sources will be merged in BIFAP and included in the study, thus, there may be variation in the capture and recording of various clinical elements. Additionally, different types of data sources will be used (e.g., records from general practice and lab results from other registers) as well as different coding systems, then variables defined in different data sources may not exactly represent the same concept across data sources. Thus, heterogeneity of vaccine effectiveness estimates across data sources may be due to the underlying heterogeneity of confounding control, misclassification, or other data source factors rather than true differences in vaccine effectiveness.

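### Missing vaccine brand is to be imputed mainly from group-level determinants, with no mention of batch or the person's other dose and no within-person constraint, so false mixed-brand schedules can enter the switcher analyses

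*Protocol*

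**What the plan says.** Section 9.7.5 of the protocol lists the vaccination fields that may be missing: "date of administration, type/brand of vaccine, dose order (whether 1 st or 2 nd dose), may happen due the workload". The remedy is conditional: "If amount of missing is relevant, single stochastic imputation will be performed based on determinant of both, missing data and the value of the variable". On the predictors it adds: "Mainly, calendar month or week, region and prioritised group will be tested as determinant of missing and will established for the imputation". It then argues that multiple imputation may not be worth its complexity if simple determinants are found.

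Four other sections bear on this:

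- Section 9.1.1.3, on the data held: "Vaccination data for each patient will include the vaccination date, dose, name of the vaccine, brand and batch for each jab".
- Section 9.1.1.4, on the main analysis of the period from day 15 after the full series: "Analysis will be performed by vaccine brand".
- Section 9.7.3.2, on a person who later receives a different vaccine: the person "will be considered switcher from the date that the last dose was received and analysed as switchers". It continues: "Among switchers, each combination of vaccines will be analysed separately".
- Section 9.9, on expected data quality: "the likelihood of missing data on specific vaccine brand may be high".

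Section 9.3.1 plans a look at dose intervals to detect double recording. No section plans a check that brands agree within a person.

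**The concern.** The issue is which information fills the gap, not how many imputations are drawn. Calendar time, region and prioritised group predict the brand mix in a stratum. They do not say which brand a given person received. For someone with brand A recorded at dose 1 and no brand at dose 2, a draw from the stratum mix can return brand B. Section 9.7.3.2 would then take that person out of brand A from the date of dose 2 and place them in an A-then-B group.

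Two things are at stake. The brand-specific windows after dose 2, which carry the main analysis, lose true completers. The mixed-schedule groups gain people who in fact had a single-brand schedule, so each combination's estimate is pulled towards single-brand effectiveness. Drawing more imputations from the same predictors would not remove this, because every draw would contain such mismatches.

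**Working it through.** There is no protocol figure to reproduce: no missing fraction, brand share or switch rate is given. Every input below is an assumption.

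**Inputs (assumed)**

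- Brand shares p_k within an imputation stratum, three two-dose brands: 95/3/2, 90/5/5 or 70/20/10.
- Fraction m of dose-2 brands missing: 5%, with 1% as a low case.
- True switching s: 1% of completers.

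**Step 1. Chance that a drawn dose-2 brand differs from dose 1** for a true single-brand recipient, when the draw uses the stratum mix only: H = 1 − Σp_k².

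- 95/3/2: 1 − (0.9025 + 0.0009 + 0.0004) = 0.096
- 90/5/5: 1 − (0.81 + 0.0025 + 0.0025) = 0.185
- 70/20/10: 1 − (0.49 + 0.04 + 0.01) = 0.46

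**Step 2. Completers made false switchers:** F = m × H.

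**Step 3. False share of apparent switchers:** F / (F + s). This ignores the few true switchers whose own missing brand is drawn wrongly.

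| Shares | m | F | F / (F + 1%) |
|---|---|---|---|
| 95/3/2 | 1% | 0.10% | 9% |
| 95/3/2 | 5% | 0.48% | 32% |
| 90/5/5 | 5% | 0.93% | 48% |
| 70/20/10 | 5% | 2.3% | 70% |

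**Step 4. Brand missing at either dose.** If each dose's brand is missing independently with probability m and drawn without regard to the other, F = [1 − (1 − m)²] × H. At m = 5% the bracket is 1 − 0.9025 = 0.0975. That gives 0.0975 × 0.096 = 0.94% at 95/3/2 and 0.0975 × 0.46 = 4.5% at 70/20/10. A simulation of 400,000 persons per scenario agreed with the formula to within 0.04 percentage points.

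**Step 5. With the other dose used.** In the same simulation, a missing brand was filled from the other dose when that was known, and drawn once per person when both were missing. False mixed schedules among true single-brand recipients fell to 0% in every scenario. This shows where the error comes from. It does not recommend copying, which would hide a true switch with one brand unrecorded.

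**Dose order.** A wrong order moves person-time between the dose-1 and dose-2 windows of section 9.1.1.4 and could shift a switch date. It does not change a brand, so it adds nothing to the figures above.

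**The case against.** The strongest reply is that the predictor list is open. It begins with a qualifier, its members are still to be tested, and the general rule admits anything that determines the missing value, which would include batch and the other dose's brand. A reader might infer that the protocol excludes within-person information. It does not; it fails to name it. The full imputation model may also be left to an analysis plan that is not shown. This stands as a limit on the wording. It does not dispose of the point: the protocol fixes the method, names the main predictors, suggests simple ones suffice, and has nothing to keep an imputed brand out of the switcher rule.

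Other replies also stand in part:

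- **Trigger.** Imputation happens only if missingness is relevant, and section 9.7.5 expects good recording. The warning in section 9.9 comes in a sentence about coding for future vaccines. False schedules are therefore possible, not certain.
- **Concentration.** The relevant mix is the one within a stratum, which may be dominated by one brand. A reader might infer that most apparent switchers would be false. At 95/3/2 that is not so: 32% at 5% missing, 9% at 1%.
- **Dose order.** Nothing says order would be drawn at random when both dates are recorded, and a wrong order cannot create a mixed-brand schedule.
- **Prioritised group.** Sections 9.7.4.1 and 9.9 say job and type of residence are not available, so one might infer that this predictor is unusable. But section 9.7.4.1 makes the remark about selecting unvaccinated people, section 9.1.1.3 leaves the first priority groups out of the study, and the figure defining the groups is not visible. At most the predictor is only partly observable.
- **Importance.** Switchers are not among the objectives in section 8.

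**Conclusion.** The point holds in a limited form. Followed as written, section 9.7.5 can give single-brand recipients a false second brand, and section 9.7.3.2 would analyse them as switchers. Both conditions are needed: enough missingness to trigger imputation, and brands mixed within strata.

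With 5% of dose-2 brands missing and 1% true switching, about 0.5% to 2.3% of completers are misassigned, and they make up roughly 32% to 70% of apparent switchers. All of this rests on assumed shares, missingness and switch rate; with less missing or one dominant brand it shrinks.

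The harm falls mainly on the switcher analyses, where true numbers may be small. A reader might infer that the main brand-specific estimates are seriously compromised. The figures do not support that: losing 0.5% to 2.3% of completers costs little precision, and a draw unrelated to outcome within strata gives no evident reason for material bias in the brand estimate.

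**What to change.** In section 9.7.5:

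1. Before any imputation, set a missing brand from the batch recorded for the same jab, where present, and set dose order from the recorded dates.
2. For brands still missing, include the other dose's brand, dose number, dose interval and age as predictors, alongside calendar time and region.
3. Count a person as a switcher under section 9.7.3.2 only when both brands are recorded or batch-derived.

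The cost is a batch-to-brand lookup and a short derivation on data the protocol already plans to hold. There are two drawbacks. Some true switches with one unrecorded brand and no batch will be missed. The yield of batch is unknown, because the protocol does not say how often it is present when brand is absent; the feasibility stage could report that cross-tabulation.

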## **9.8 Quality Control**

Quality control, rules for secure and confidential data storage, methods to maintain and archive project documents, quality-control procedures for programming, standards for writing analysis plans, will be performed according to the BIFAP governance that can be consulted in the following linked of BIFAP website [68].

## **9.9 Limitations of the Research Methods**

Although this protocol addresses many design considerations to avoid common biases of vaccine effectiveness research, studies of COVID-19 vaccines may be subject to many of the limitations common to non-randomised studies based in existing health care data.

Patient's test-seeking behaviour may be associated with both severity of infection symptoms and personal health-seeking behaviour, which may introduce selection bias or confounding [28,29].

Confounding of the relationship between vaccine receipt and COVID-19 outcomes may be very likely, and spurious relationships between vaccine receipt and implausible outcomes have been noted in other studies comparing vaccine recipients to non-recipients. The use of eligibility criteria to define comparable exposure groups, covariates

based on updated subject-matter knowledge will allow investigators to adequately address confounding through the design and analysis.

The baseline clinical history of individuals in the initial priority groups (i.e. health care workers and people living in nursing home) may not be systematically included in BIFAP eHR. Thus, many of them may not be up-to-standard for research as explained above and power limitation may be expected.

Even though efforts will be done for proper control of bias and multivariate adjustment minimizing confusion, no information about the job and type of residence will be available. Consequently, confusion may still be present due to the higher probability of infection among them versus other social groups. That aspect would direct towards a reduction in the effectiveness estimations.

If data about determinants, such as personal health-seeking behaviour, would not be recorded in the database, the selection of patients included in the compared groups and/or their dates to start the comparison could be biased, i.e.

- Patients prone to infections or to develop a severe/hospitalised infection or those with active respiratory infection/disease (prevalent active pneumonia, COPD, etc) decided to attend to receive the vaccination earlier/more than those less prone to it, we could observe patients more affected by covid among the vaccinated group. That aspect would direct towards a biased lower effectiveness estimation due to selection bias).
- The opposite could also be true, i.e. patients more adhered to general prevention measured (personal health-seeking behaviour such as applying social distance, wearing mask, volunteer confinement, etc) were more vaccinated we could be observing more covid infections in the unvaccinated group. That aspect would direct towards a biased higher effectiveness estimation due to selection bias.

Selective recruitment into the study of vaccinated/unvaccinated subjects from those recorded in the database with quality criteria (up-to-standard information) that are not representative of the general vaccinated/unvaccinated subjects respectively in the source population could produce selection bias. For instance:

- If we were losing people having died from coronavirus disease even though they were vaccinated (i.e. non effective vaccinations), selection bias would be present. Similarly, if more vaccinated participants were survivors of previous covid infections than vaccinated non-participants (example, they died by covid) because those attend the PCP (having information and minimum anamnesis in the database required to participate) while vaccinated non-participants do not.
- Also, If vaccinated participants were recorded in the database because they are more closely surveyed by the PCP/nurse due to their predisposition to complicated COVID infection (i.e. baseline health conditions), while vaccinated

non-participants were not recorded in the database because they do not seek healthcare, we would be including in the study patients with more probability to severe infection than the real overall vaccinated individuals

The selection bias could direct towards any direction the effectiveness estimates.

if an individual's personal health beliefs and behaviours increase the likelihood of both COVID-19 vaccines receipt and seeking health care for milder disease, then the analysis of this outcome may be particularly subject to confounding by health care-seeking behaviour.

The validity of coding for future COVID-19 vaccines—including the ability to distinguish between separate products—or COVID-19 outcomes is unknown at this time, and the likelihood of missing data on specific vaccine brand may be high. Misclassification of vaccine exposure, outcome status, or covariates is possible in existing health care data not collected for research purposes. Information about COVID-19 infection (through test results or codes) may not be captured reliably in databases. Additionally, COVID-19 testing is not systematic, and laboratory confirmation of case status may not be available for many patients. Currently, bias may be minimised since COVID 19 testing becomes near universal and repeated with individuals, with similar testing capacity and practice across regions, though. Since we will not have any better gold-standard for case status than the information about confirmed covid-19 infection through lab results (used for case definition in the current study) its precision will not be evaluated but with the expected external incidences published by the Health authorities.

Also, we consider that if COVID misclassification occurred it would be similar in both, vaccinated and unvaccinated groups, however surveillance or detection bias (different likelihood of screening or testing for COVID between the groups) cannot be discarded. If vaccinated individuals had less likelihood of screening or test than unvaccinated, we would artificially observe more cases among unvaccinated, directing toward a biased higher vaccine effectiveness estimation.

Data from multiple regions and sources will be merged in BIFAP and included in the study, thus, there may be variation in the capture and recording of various clinical elements. Additionally, different types of data sources will be used (e.g., records from general practice and lab results from other registers) as well as different coding systems, then variables defined in different data sources may not exactly represent the same concept across data sources. Thus, heterogeneity of vaccine effectiveness estimates across data sources may be due to the underlying heterogeneity of confounding control, misclassification, or other data source factors rather than true differences in vaccine effectiveness.

Patterns of routine health care delivery and utilisation may be disrupted during the COVID-19 pandemic as patients and providers forgo or delay routine preventive, elective, or non-emergency care. These disruptions in health care may result in under-

ascertainment of important patient comorbidities in existing health care databases during periods of disruption.

In order to conduct a valid study and address potential confounding, the eligibility criteria of the study will be restricted relative to the approved indications of the vaccines. Therefore, the results of this study may not be generalisable to the general population but to the restricted population.

With the introduction of a new vaccine, there is the potential for rapidly changing herd immunity in the population. This study is not designed to assess overall and indirect effects of vaccination with COVID-19 vaccines.

Comparative analyses may not be possible in every setting if confounding is deemed to be insurmountable. However, descriptive information about vaccine recipients and crude incidence rates may still be informative and meaningful, even without calculation of vaccine effectiveness measures.

The capture of over-the-counter medications, potentially indicative of short-term disease status (e.g., painkillers, cough medicines, and fever reducers) may not be captured reliably.

